^bPlasma drug concentrations will be measured at a feasible time only for early termination/withdrawal.

^cMeasurement of serum sodium and potassium concentrations during the treatment period will be performed at both the central laboratory and the trial site. If it is difficult to perform serum sodium and potassium concentration measurement at the trial site, plasma sodium and potassium concentrations may be

measured. Either serum or plasma should be used consistently for measurement of sodium and potassium concentrations in a given subject. However, even if plasma sodium and potassium concentrations are measured at the trial site, serum sodium and potassium concentrations will be measured at the central laboratory.

^dBiomarkers: Plasma concentrations of AVP, BNP, plasma renin activity, and serum concentrations of NT-proBNP and troponin I

^eCongestive symptoms: Lower limb edema, jugular venous distension, hepatomegaly, pulmonary rales, and cardiac third sound

^fChest x-ray: cardiothoracic ratio and pulmonary congestion

If chest x-ray has been performed at a regular visit prior to participation in the present trial (within 14 days before informed consent), assessment of cardiothoracic ratio and pulmonary congestion at screening may be performed based on that previous chest x-ray without having to perform a new chest x-ray.

^gTiming of 12-lead ECG: Before breakfast and at 1 to 2 hours postdose on Day 1 and at a feasible time at other time points. If the serum potassium concentration at the trial site or the central laboratory is confirmed to exceed 5.5 mEq/L at any time point with no scheduled 12-lead ECG during the treatment period, an additional 12-lead ECG will be performed as an unscheduled examination.

^hDNA storage: In principle, blood sampling for DNA storage will be performed on the day of initial IMP administration (Day 1). Informed consent to DNA storage should be obtained before blood sampling for DNA storage. If blood sample cannot be collected or re-collection is required, blood sampling will be repeated at a feasible time during the trial period.

Table 3.7-2 Allowable Time Window for Examinations/Tests and Blood Sampling After IMP Administration on Day 1	
Item	Timing
Plasma drug concentrations	60 to 75 minutes after start of IMP administration
	4 to 6 hours after start of IMP administration
	8 to 12 hours after start of IMP administration

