3.7.1.4 Treatment Period (Day 1)

1) Before breakfast

- Serum sodium concentration, serum potassium concentration, serum osmolality, and biomarkers
- Body weight
- Clinical laboratory tests
- Vital signs (blood pressure, pulse rate, and body temperature)
- 12-Lead ECG
- Blood sampling for DNA storage (DNA storage is optional. Informed consent should be obtained before blood sampling for DNA storage.)

2) After breakfast

Subject are required to urinate completely immediately after breakfast, and urine collection and fluid intake measurement will start to assess the following items from the point at which urination immediately before IMP administration has been completed.

- Daily urine volume, daily fluid intake, and daily fluid balance
- Daily urine sodium excretion and daily urine potassium excretion
- Urine osmolality

3) IMP administration

The investigator or subinvestigator will confirm that the subject meets all of the inclusion criteria and falls under none of the exclusion criteria, administer the IMPs to the subject, and enter the status of IMP administration into the IWRS.

4) After IMP administration

The investigator or subinvestigator will conduct the following examinations.

- Blood sampling for measurement of the plasma drug concentrations: 60 to 75 minutes, 4 to 6 hours, and 8 to 12 hours after start of IMP administration
- Serum sodium concentration and serum potassium concentration: 4 to 6 hours and 8 to 12 hours after start of IMP administration
- 12-Lead ECG: 1 to 2 hours after start of IMP administration

5) At a feasible time

- Congestive symptoms (lower limb edema, jugular venous distension, hepatomegaly, pulmonary rales, and cardiac third sound)
- Adverse events, physical examination
- Concomitant medications and therapies
- Confirmation of IMP compliance

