3.7.3.3 Physical Examination and Vital Signs

1) Physical examination

The investigator or subinvestigator will check the physical conditions of the subject by interview and other methods at the prespecified time points. The physical examination includes the observation of the head, ears, eyes, nose and pharynx, chest, abdomen, genitourinary tract, extremities, nerves, and skin/mucosae. At the screening examination, the date and the results of assessment will be recorded in the source document and the eCRF. At subsequent assessments, only the date of assessment will be recorded in the source document and the eCRF. A clinically important physical

finding that is absent at the screening examination but observed at any post-treatment assessment will be recorded as an AE.

2) Vital signs (blood pressure, pulse rate, and body temperature)

At the prespecified time points, axillary temperature will be measured after the subject is kept rested according to the procedures specified by the trial site. Blood pressure (systolic and diastolic) and pulse rate will be measured after the subject is kept supine for at least 3 minutes. The measurement result of body temperature should be rounded to the first decimal place for recording, even if the measurement result is shown the second decimal place or more. The date and time, and the results of measurements will be recorded in the source document and the eCRF.

3.7.3.4 12-Lead Electrocardiogram Assessments

At the prespecified time points, a rest 12-lead electrocardiogram (ECG) will be recorded using the ECG monitor provided by the central ECG measurement facility and according to the procedure specified by the facility. However, if the serum potassium concentration at the trial site or the central laboratory is confirmed to exceed 5.5 mEq/L at any time point with no specified 12-lead ECG during the treatment period, an additional 12-lead ECG will be performed as an unscheduled examination. The investigator or subinvestigator will interpret each ECG chart as normal or abnormal, and record the status (measured/ not measured), the date of recording, as well as the interpretation (normal or abnormal [details, if abnormal]) in the source document and the eCRF.

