The ECG record will be sent to the central ECG measurement facility to measure the heart rate, RR interval, PR interval, QRS axis, QT interval, and QTc (QT corrected for heart rate) interval (QTcB, QTcF). The central ECG measurement facility will in turn send the 12-lead ECG analysis report to the investigator or subinvestigator.

The investigator or subinvestigator will reconfirm the interpretation of the 12-lead ECG referring to the analysis report, which will then be signed and retained.

The electronic file of the 12-lead ECG analysis report provided to the sponsor by the central ECG measurement facility will be used as the source document; therefore, entry of the heart rate, RR interval, PR interval, QRS axis, QT interval, and QTc interval (QTcB, QTcF) in the eCRF will be unnecessary.

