3.4 Handling of Time Points

Case report form (CRF) Visit values at each time point (run-in period, treatment period, and follow-up) will be used in summaries (but values at the time of discontinuation will not be used in summaries). Unscheduled Visit values will not be used.

Baseline and final administration time point for each variable are defined as follows.

Variable	Baseline ^a	Final Administration Time Point
Body weight	Before IMP administration on Day 1	Day after final IMP administration
Congestive symptoms (lower limb edema, jugular venous distension, hepatomegaly, pulmonary rales, third cardiac sound)	Run-in period (final measurement)	Day after final IMP administration
Pulmonary congestion, cardiothoracic ratio	Run-in period	Day after final IMP administration
NYHA classification	Run-in period	Day after final IMP administration
Clinical laboratory value	Before IMP administration on Day 1	Day after final IMP administration
Vital signs	Before IMP administration on Day 1	Day after final IMP administration
12-lead ECG	Before IMP administration on Day 1	Day after final IMP administration
Serum sodium concentration, serum potassium concentration, serum osmolality, biomarker	Before IMP administration on Day 1	-
Daily urine volume, daily fluid intake, daily fluid balance, daily urine sodium excretion, daily urine potassium excretion, urine osmolality	Within 24 hours before start of IMP administration on Day 1	-

^aWhen multiple data are collected during the run-in period, the data closest to Day 1 will be used as baseline.

4 Sample Size

The number of subjects required to confirm the non-inferiority of OPC-61815 16-mg injection to tolvaptan 15-mg tablet for the primary endpoint of change in body weight from baseline (before IMP administration on Day 1) at the time of final IMP administration (day after final IMP administration) was determined.

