9.6 Electrocardiogram Data

For 12-lead ECG parameters, measured values and changes from baseline at each time point and at the time of final IMP administration will be summarized using descriptive statistics.

The numbers and percentages of subjects who have a QTc interval (QTcF) of >450, 480, or > 500 msec at any post-treatment time point until the time of final IMP administration will be calculated. The numbers and percentages of subjects who have a change in QTc interval from baseline of >30 and >60 msec at any post-treatment time point and at the time of final IMP administration will be calculated. Also at baseline and at each post-treatment time point, the numbers and percentages of subjects will be calculated in the same manner as described above.

Shift tables for QTcF interpretation (normal or abnormal) will be prepared at each post-treatment time point and at the time of final IMP administration compared with baseline. Interpretation (normal or abnormal) assessments by the trial site (investigator or subinvestigator) will be used instead of the assessments by the central ECG analysis laboratory.

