CT-10.5 Incidence of Potential Drug-Induced Liver Injury (Safety Analysis Set)

CT-11 Mean Change from Baseline in Vital Signs (Safety Analysis Set)

CT-12.1 Mean Change from Baseline in Electrocardiogram Results (Safety Analysis Set)

CT-12.2 Shift Table of 12-Lead ECG Findings (Normal/Abnormal Assessments) (Safety Analysis Set)

CT-12.3.1 Incidence of Categorical Changes in Electrocardiogram Results (Post baseline any visit) (Safety Analysis Set)

CT-12.3.2 Incidence of Categorical Changes in Electrocardiogram Results (Each Visit) (Safety Analysis Set)

PDT-1.1 Descriptive Statistics for Daily Urine Volume (mL) With Confidence Interval for Treatment Difference (Pharmacodynamic Analysis Set)

PDT-1.2 Mean Change for Daily Urine Volume (mL) With Confidence Interval for Each Treatment Group (Pharmacodynamic Analysis Set)

PDT-2 Descriptive Statistics for Daily Fluid Intake (mL) With Confidence Interval for Treatment Difference (Pharmacodynamic Analysis Set)

PDT-3 Descriptive Statistics for Daily Fluid Balance (mL) With Confidence Interval for Treatment Difference (Pharmacodynamic Analysis Set)

PDT-4 Descriptive Statistics for Serum Sodium Concentration (mEq/L) (Pharmacodynamic Analysis Set)

PDT-5 Descriptive Statistics for Serum Potassium Concentration (mEq/L) (Pharmacodynamic Analysis Set)

PDT-6 Descriptive Statistics for Serum Osmolality (mOsm/kg) (Pharmacodynamic Analysis Set)

PDT-7 Descriptive Statistics for Plasma AVP Concentration (pg/mL) (Pharmacodynamic Analysis Set)

PDT-8 Descriptive Statistics for Plasma BNP Concentration (pg/mL) (Pharmacodynamic Analysis Set)

PDT-9 Descriptive Statistics for Plasma Renin Activity (ng/mL/hr) (Pharmacodynamic Analysis Set)

PDT-10 Descriptive Statistics for Serum pro BNP Concentration (pg/mL) (Pharmacodynamic Analysis Set)

PDT-11	Descriptive Statistics for Serum Troponin Concentration (pg/mL) (Pharmacodynamic Analysis Set)
PDT-12	Descriptive Statistics for Daily Urine Excretion of Sodium (mEq) (Pharmacodynamic Analysis Set)
PDT-13	Descriptive Statistics for Daily Urine Excretion of Potassium (mEq) (Pharmacodynamic Analysis Set)
PDT-14	Descriptive Statistics for Urine Osmolality (mOsm/kg) (Pharmacodynamic Analysis Set)
CF-1	Transition Diagram for Body Weight (Full Analysis Set)
CF-2	Transition Diagram for Improvement Rate of Lower Limb Edema (Full Analysis Set)
CF-3.1	Transition Diagram for Jugular Venous Distension (cm) (Full Analysis Set)

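### SAP 3.4 excludes unscheduled values without exception, so ECGs triggered by high potassium may be missing from the any-time QTc counts (CT-12.3.1)

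*SAP*

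**What the plan says.** SAP 3.4 bases summaries on CRF visit values, then sets two exclusions: "values at the time of discontinuation will not be used in summaries). Unscheduled Visit values will not be used". Neither is limited to a type of table.

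The protocol creates an ECG outside the visit schedule. Note g to Table 3.7-1 applies when potassium exceeds 5.5 mEq/L "at any time point with no scheduled 12-lead ECG during the treatment period". Protocol 3.7.3.4 repeats the requirement: "an additional 12-lead ECG will be performed as an unscheduled examination". The same section covers central reading: "The ECG record will be sent to the central ECG measurement facility to measure the heart rate".

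SAP 9.6 counts patients with QTcF above each limit "at any post-treatment time point until the time of final IMP administration will be calculated". It treats QTc changes above 30 and 60 msec in a similar way. Protocol 7.6.4 defines the same counts and excludes nothing. SAP Appendix 1 plans two tables. CT-12.3.1 is titled "Incidence of Categorical Changes in Electrocardiogram Results (Post baseline any visit" and CT-12.3.2 is titled "Incidence of Categorical Changes in Electrocardiogram Results (Each Visit". SAP 14 declares no change from the planned analyses.

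**The concern.** A triggered ECG is taken because a safety value was abnormal, so leaving it out is not a random loss. Excluding off-schedule readings suits a visit-by-visit table, where every patient should contribute the same planned readings. It suits a table meant to show whether a limit was ever crossed much less well. A patient whose only QTcF above 500 msec came from a triggered ECG would appear in a listing but not in the count. The protocol's definition of these counts would also have been narrowed without being declared in SAP 14.

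The liver count in SAP 9.3 (CT-10.5: bilirubin together with AST or ALT) is also defined over all post-treatment time points, so the same sentence reaches any unscheduled central panel.

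**Working it through.** The SAP gives no figure on this point. The check is a reading of the text followed by a sizing.

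**1. Is there an exception?** SAP 9.3 and 9.6 do not readmit unscheduled values. SAP 5.5 only replaces a missing final assessment. SAP 14 is empty. SAP 5.5 carries the missing-data wording that Amendment 2 introduced into protocol 7.3, so the SAP appears to follow the amendment that added the ECG trigger. SAP 3.4 still does not address the triggered ECG.

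**2. Where can the trigger fire?** For Day 1 the protocol lists "Serum sodium concentration and serum potassium concentration: 4 to 6 hours and 8 to 12 hours after start of IMP administration". Protocol 3.7.1.5 to 3.7.1.8 add a potassium sample on each of Days 2 to 6.

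| Post-dose potassium time point | ECG scheduled then? |
|---|---|
| Day 1, 4–6 h | No (the Day 1 post-dose ECG is at 1–2 h) |
| Day 1, 8–12 h | No |
| Day 2 | No |
| Day 3 | Yes |
| Day 4 | No |
| Day 5 | No |
| Day 6 | Yes |

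That is 5 of 7 time points without a scheduled ECG. Counted by day it is 3 of 6 (Days 2, 4 and 5). These are opportunities, not events. All five fall inside the SAP 9.6 window, because SAP 3.4 sets the final administration time point at the day after the last dose.

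**3. How many patients fall under the trigger?** Amendment 2 is dated 27 March 2020, and the synopsis plans conduct from January 2019 to July 2020. Taking the first and last days of those months:
- 1 Jan 2019 to 31 Jul 2020: 365 + 213 = 578 days
- 27 Mar to 31 Jul 2020: 5 + 30 + 31 + 30 + 31 = 127 days
- Share: 127/578 = 22.0%
- Patients, if enrolment was even: 288 × 0.220 ≈ 63

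This is an upper figure under that assumption, since protocol section 13 requires IRB approval before a change of this kind is implemented.

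**4. How many triggered ECGs?** The documents give no rate of potassium above 5.5 mEq/L at these points, so the rates are assumed:
- 2%: 63.3 × 0.02 = 1.3 patients
- 5%: 63.3 × 0.05 = 3.2 patients
- 10%: 63.3 × 0.10 = 6.3 patients

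**5. How many miscounted?** A patient is miscounted only if the triggered ECG crosses a limit that none of that patient's scheduled post-dose ECGs (Days 1, 3 and 6) crosses. If 10% to 20% of triggered ECGs did so (a second assumption, for illustration), the range is 1.3 × 0.10 = 0.1 to 6.3 × 0.20 = 1.3 patients over both arms.

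**6. Effect on a reported rate.** One patient is 1/144 = 0.69 percentage points of an arm. Moving from 0/144 to 1/144 raises the upper exact 95% limit from 2.5% to 3.8%.

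**7. Liver panels.** Post-dose panels are scheduled only at Day 6 or withdrawal and at follow-up (Table 3.7-1). Protocol 5.1 permits repeat or additional tests but names no laboratory. The number of unscheduled central panels cannot be estimated.

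**The case against.** The strongest objection is that the two documents use different terms. The SAP excludes values from an unscheduled visit; the protocol calls the ECG an unscheduled examination. Patients are inpatients through Day 6, so a triggered ECG on Day 2, 4 or 5 falls on a scheduled trial day and might be stored under that day's visit. The CRF design is not in the documents. This stands: a reader might infer that these ECGs are certainly dropped, and the text supports only that they would be if stored as unscheduled visits.

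Second, an any-visit table restricted to scheduled visits is coherent and gives both arms equal opportunity to register an exceedance. That is a defensible choice. But neither SAP 9.6 nor the protocol states it for this table, and CT-12.3.2 already serves the purpose.

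Third, protocol 3.7.3.2 says the ECG is done as necessary, which sounds optional. It refers to 3.7.3.4, where the ECG is required, so this carries little weight.

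Fourth, a reader might infer that liver signals are lost. The documents do not support that. No unscheduled central panel is mandated. The bilirubin that protocol 5.4 asks for is already in the same central panel as AST and ALT (Table 3.7.3.2-1). Site results are excluded by the separate central-only rule in SAP 9.3. The liver part is therefore conditional.

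Fifth, a reader might take the discontinuation clause to remove early withdrawals from the primary analysis. The table in SAP 3.4 and SAP 5.5 both point to the value on the day after the last dose, so the sensible reading limits the clause to by-visit summaries.

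**Conclusion.** The point holds in conditional form. SAP 3.4 has no exception, and a programmer following it would drop potassium-triggered ECGs from CT-12.3.1 if the CRF records them as unscheduled visits. The size is small: most likely no more than one or two patients in the whole trial, given even enrolment, a 2% to 10% trigger rate and the illustrative crossing rate, none of which the documents supply.

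The gap is in the summary counts only. Central ECG results are listed (PDATA-6.1), potential liver injury is listed (CT-10.4.2), and combined liver elevations are reported as immediately reportable and adverse events (protocol 5.4). Nothing here touches detection, reporting or the primary endpoint. Severity is minor; confidence is moderate because of the storage question.

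**What to change.** In SAP 3.4:

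1. Limit the exclusion of unscheduled and discontinuation values to by-visit descriptive summaries, shift tables and CT-12.3.2.
2. State that all post-dose central readings, including unscheduled and withdrawal ones, count in the any-time analyses within each analysis's stated window. These are CT-12.3.1 and, where such panels exist, CT-10.5.
3. Confirm that the withdrawal assessment on the day after the last dose supplies the final-administration value.

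The central-only laboratory rule stays as it is. The cost is three sentences and minor programming, with no new data collection, because ECG records already go to the central facility. The downside is that patients with triggered tests contribute more readings than others, so counts may rise slightly. CT-12.3.2 keeps the comparison on scheduled visits.

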5.1 Full Analysis Set

The full analysis set (FAS) includes all subjects who received at least one dose of IMP and have evaluable post-treatment body weight data.

5.2 Safety Analysis Set

The safety analysis set includes all subjects who received at least one dose of IMP.

5.3 Pharmacodynamic Analysis Set

The pharmacodynamic analysis set includes all subjects who received at least one dose of IMP and have evaluable post-treatment pharmacodynamic data.

5.4 Pharmacokinetic Analysis Set

Of the subjects in the safety analysis set, those with measured plasma drug concentration data will be included in the pharmacokinetic analysis set.

5.5 Handling of Missing Data

If the data at the time of final assessment (on the day after final IMP administration) is missing, the last available data obtained by the day after final IMP administration will be used (efficacy and safety).

6 Primary and Secondary Outcome Variables:

6.1 Primary Outcome Variables

Change in body weight from baseline at time of final IMP administration (day after final IMP administration)

6.2 Secondary Outcome Variables

- Congestive symptoms (lower limb edema, pulmonary congestion, jugular venous distension, hepatomegaly, cardiothoracic ratio, pulmonary rales, and cardiac third sound)
- New York Heart Association (NYHA) classification

7 Disposition and Demographic Analysis

The following will be summarized by treatment group (excluding subjects from whom informed consent was obtained).

7.1 Subject Disposition

For subjects from whom informed consent was obtained (screened subjects), the number of subjects and randomized subjects and the numbers and percentages of subjects administered IMP, completed subjects after IMP administration, and discontinued subjects after IMP administration (the denominator indicates the number of randomized subjects) will be summarized. For discontinued subjects after IMP administration, the number and percentage of subjects by reason for discontinuation will be summarized.

For randomized subjects, the number and percentage of subjects included in each statistical analysis set will be summarized.

7.2 Demographic and Baseline Characteristics

For the full analysis set and safety analysis set, descriptive statistics (number of subjects, mean, SD, minimum, median, and maximum, the same applies hereinafter to Chapter 9) or distributions (number of subjects, %, the same applies hereinafter) will be calculated according to [Table 7.2-1](#).

Table 7.2-1 Demographic and Other Baseline Characteristics			
Variable	Time Point	Method	Level
Age	Informed consent acquisition	Descriptive statistics	-
		Distribution	20-29, 30-39, 40-49, 50-59, 60-69, 70-79, 80-85
			<65, ≥65
Sex	-	Distribution	Female, Male, Undifferentiated
Height (cm)	Screening	Descriptive statistics	-
Body weight (kg)	Screening	Descriptive statistics	-
BMI (kg/m ²)	Screening	Descriptive statistics	-
Country	-	Distribution	JAPAN
Race	-	Distribution	Asian
Ethnicity	-	Distribution	Not Hispanic or Latino
Primary illness (multiple selection) • Ischemic heart disease • Cardiomyopathy • Valvular disease • Hypertensive heart disease • Arrhythmia	Screening	Distribution	Yes, No
Type of heart failure	Screening	Distribution	Right Heart Failure, Left Heart Failure, Bi-ventricular Failure, Unspecified
Presence of arrhythmia	Screening	Distribution	Yes, No
Use of Pacemaker	Screening	Distribution	Yes, No
Use of ICD	Screening	Distribution	Yes, No
Complication (multiple selection) • Hypertension • Angina pectoris • Diabetes mellitus • Renal impairment	Screening	Distribution	Yes, No
Presence of complication	Screening	Distribution	Yes, No
Presence of medical history	Screening	Distribution	Yes, No

